3.1 Subject Entry

Prior to enrollment in the study, the subject will be evaluated to determine eligibility. All inclusion criteria and no exclusion criterion will be met by an eligible subject. The investigator will explain the study purpose, procedures, and patient responsibilities to the potential participant. The subject's willingness and ability to meet the follow-up requirements will be determined.

When it has been established that the subject may be eligible, written informed consent will be obtained. The subject will sign and date the informed consent form in the presence of a witness. The investigator or designees will also sign and date the consent form. The original will be retained with the subject records and a copy will be provided to the subject. An affidavit of Informed Consent (Appendix C) will be completed and returned to ViaLase to confirm that consent was obtained. The subject will then be considered enrolled in the study.

3.2 Informed Consent

In accordance with GCP, the Investigator is responsible for fully reviewing the nature of the study, the possible risks, and alternative treatments with prospective subjects prior to their enrollment in the study. The Investigator is responsible for obtaining written Informed Consent for each subject, prior to enrollment in the trial. A copy of the signed Informed Consent Form will be maintained in the subject's medical record or research chart, and a copy of the signed Informed Consent Form will become an integral part of each Case Report file provided to the Sponsor.

3.3 Preoperative Evaluation

Preoperative evaluation consists of two patient visits, a screening visit, and a baseline visit. During the screening visit, occurring 1 to 30 days prior to the baseline visit, the investigator informs the subject of the study and, after the subject provides consent, the investigator collects initial subject data including the subjects, demographics, ocular history, a list of ocular and non-ocular medications, and medical history. The investigator will also assess the subjects corrected visual acuity and perform a slit lamp examination.

During the baseline visit, occurring 3 to 60 days prior to the operative day, the investigator confirms the subject's list of ocular and non-ocular medications. The investigator then performs manifest refraction, best corrected spectacled visual acuity, and an endothelial cell count.

3.4 Preoperative Care

Subjects included in this study present with uncontrolled refractive Primary Open Angle Glaucoma (POAG) using 1 or more IOP lowering medications. Included subjects will be instructed to continue all current glaucoma medication.

This section has been redacted of company proprietary information

This section has been redacted of company proprietary information

3.3 Postoperative Instructions

Refer to Appendix B for complete instructions associated with Methods of Clinical Evaluation.

- 1. Following surgery, the investigator or designee will instruct subjects to adhere to the following antibiotic/anti-inflammatory medication regimen for the study eye only:
 - a. Topical antibiotic that is utilized as investigator's routine postop regiments.
 - b. Continuation of glaucoma medications.
- During the study, the discontinuation or a reduction in the dose or frequency of topical IOP lowering medication may be warranted whenever it is in the interest of patient safety.
 Conditions that may warrant discontinuation or frequency reduction in medication include hypotonous condition, an adverse reaction, or other systemic side effect.
- 3. If a pressure rise is observed, a paracentesis may be performed, as necessary. If a paracentesis is performed and there is no protocol-defined adverse event, the paracentesis will be documented in the applicable clinical report form (CRF). If, however, the paracentesis is performed and an anticipated adverse event is determined, then the AE will be recorded, and the paracentesis will be recorded on the applicable CRF as a treatment for the AE.

3.4 Examination Schedule:

Follow-up visits (as shown in Appendix A) will be scheduled over the course of 6 months. A CRF will be completed for each scheduled, unscheduled, and interim exam. Scheduled visits are defined as visits outlined in the schedule of visits. Interim visits are defined as study related visits deemed necessary by the protocol or the PI that are in addition to scheduled visits, and unscheduled visits are defined as visits that are not scheduled or interim. Subjects will be examined and evaluated according to the following scheduled visits:

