3.7 Adverse Events

3.7.1 Recording Adverse Events

If adverse events (AEs) occur, the first concern will be the welfare of the subject, including any treatment the Investigator believes is appropriate.

Adverse events that occur during the trial whether they are device related or not, will be documented. An adverse event is defined as any **clinically significant** new or changed untoward condition, or a condition requiring treatment, either surgical or medical intervention.

- Recording of all AEs shall include the AE term and assessed relationship of the event to the study device/procedure. Additionally:
 - a. Recording of ocular AEs and related AEs shall include the start and resolution dates, severity, and treatment (if any).
 - b. Recording of non-ocular AEs that are not related to the study treatment will be limited to documenting the start and resolution dates (if any) from subject self- reports or other avenues and no additional information will be recorded.
 - c. All AEs will be documented on the AE CRF.
- 2. Postoperative inflammation within or at 30 days post-surgery will be reported as an AE for cells and flare graded as 3+ or 4+.
- 3. Ocular events occurring greater than 30 days postoperatively that meet the following criteria will be reported as AEs.
 - a. For evaluations for which a standard grading scale is available, ocular AEs will be captured for significant (2-grade) worsening.
 - b. For evaluations where a standard grading scale is not available, clinically significant events assessed as mild, moderate, or severe will be captured as AEs.
- 4. For related, systemic AEs or all ophthalmic AEs treated with surgical intervention, the intervention should be recorded in the Ocular Procedure Log as a treatment for the AE, and the interventional treatment will not be recorded as a separate AE. If a single condition results in multiple protocol defined AE's, the root cause AE will be recorded, and the other events will be recorded as sequelae. (For example, an increase in crystalline lens opacity of greater than 3 half step increments that leads to a VF Mean Deviation loss of greater than 2.5dB. The crystalline lens opacity is recorded as an AE, and the VF Mean Deviation loss is recorded as a sequela).
- 5. The severity (intensity) of AEs will be rated as follows:

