3.7.2 Adverse events knowing to occur during or after laser procedures

Specific examples of adverse events that potentially may occur during or after laser surgery (regardless of likelihood) include but are not limited to:

- Choroidal hemorrhage
- Choroidal effusion
- Cyclodialysis cleft
- Significant hyphema (i.e. ≥ 10% of anterior chamber)
- Significant iris damage

Possible postoperative adverse events:

- Allergic reaction
- Intraocular inflammation (not pre-existing) remaining or arising after the protocol's specified medication regimen is complete
- Choroidal effusion
- Choroidal hemorrhage
- Aqueous misdirection
- Chronic pain in the study eye present greater than 3 months postoperative
- Clinically significant cystoid macular edema

- Corneal abrasion
- Flat or shallow anterior chamber (e.g., shallowing of the anterior chamber that causes any amount of iris-cornea touch)
- Hypotony (IOP < 6 mmHg) associated with clinically significant findings. (Clinically significant hypotony is defined as hypotony maculopathy or hypotony with flat anterior chamber requiring reformation, corneal folds, choroidal effusions requiring drainage, and/or suprachoroidal hemorrhage)
- Increase in C/D ratio of > 0.3 units
- IOP increase requiring management with oral or intravenous medications or with surgical intervention
- IOP increase ≥ 10 mmHg vs. baseline IOP occurring at any visit
- Iridodialysis
- Loss of best spectacle corrected visual acuity (BSCVA) of 2 lines or more (logMAR scale; 10 letters or more on ETDRS chart)
- Pupillary block
- Secondary surgical intervention
- Significant corneal complications including opacification and decompensation
- Significant corneal edema (NOTE: A classification of mild to moderate corneal edema up to and including the Week 1 postoperative exam is NOT considered an adverse event)
- Significant hyphema (≥ 10% of anterior chamber)
- Vitreous hemorrhage
- Worsening in visual field of mean deviation (MD) of ≥ 2.5 dB compared to the MD used to determine subject eligibility (confirmed in at least 2 out of 3 postoperative visual field tests performed within a 90-day period)

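### Section 3.3 item 3 offers a no-AE route for a pressure rise treated by paracentesis that 3.7.1 should never let apply; if a site uses it, some treated rises below 10 mmHg go unrecorded as AEs

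*Combined protocol and SAP*

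**What the plan says.** Section 3.3 Postoperative Instructions, item 3, lets the investigator perform a paracentesis when a pressure rise is seen and the procedure is thought necessary. It gives no IOP threshold. Two recording routes follow:

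- CRF only: "If a paracentesis is performed and there is no protocol-defined adverse event, the paracentesis will be documented in the applicable clinical report form (CRF".
- AE route: if "the paracentesis is performed and an anticipated adverse event is determined, then the AE will be recorded", with the paracentesis entered on the CRF as the treatment.

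The visible text defines neither the protocol-defined AE of the first route nor the anticipated AE of the second.

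Section 3.7.1 defines an AE as a clinically significant new or changed untoward condition, "or a condition requiring treatment, either surgical or medical intervention". Its item 4 says that for ophthalmic AEs treated surgically "the intervention should be recorded in the Ocular Procedure Log as a treatment for the AE", and that the treatment is not a separate AE.

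Section 3.7.2 gives examples of AEs. Three bear on this point: "IOP increase requiring management with oral or intravenous medications or with surgical intervention"; a rise of at least 10 "mmHg vs. baseline IOP occurring at any visit"; and "Secondary surgical intervention". The visible text does not say whether paracentesis is a surgical intervention.

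Section 3.9 commits to the number and percentage of patients with any AE. It names no count of paracenteses.

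**The concern.** Item 3 starts from a pressure rise that was judged to need a procedure and then allows for there being no AE. Section 3.7.1 makes the need for treatment sufficient for an AE. The two instructions do not fit together, and a site has to choose between them.

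The study's stated objective is initial evidence of safety, and a 1-hour IOP rise is the first immediate safety outcome in 1.5.1. Whether a rise had to be relieved by a procedure is part of that evidence. Two similar treated rises could be filed differently, and the choice works in one direction: the CRF-only route can lower the any-AE percentage or leave it unchanged, but cannot raise it.

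AE status also carries obligations that item 3 does not attach to the CRF-only route: dates and severity (3.7.1 item 1), relatedness (3.7.1 item 6), tabulation by seriousness, severity, outcome and relationship (1.5.3), and follow-up of ophthalmic events (3.7.5).

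**Working it through.** The plan states no figure on this point, so there is none to reproduce. The check has two parts.

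**1. Apply each rule to a rise treated by paracentesis.** The rises are examples. The rules come from 3.7.1, 3.7.2 and 1.5.1.

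| Rise over baseline (mmHg) | AE under 3.7.1 (needed treatment) | On the 3.7.2 list if paracentesis is surgery | On the 3.7.2 list if it is not surgery | Meets the 6 mmHg outcome if present at 1 hour |
|---|---|---|---|---|
| 3 | yes | yes | no | no |
| 8 | yes | yes | no | yes |
| 9.9 | yes | yes | no | yes |
| 10 | yes | yes | yes | yes |
| 14 | yes | yes | yes | yes |

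- Under the second and third columns every treated rise is an AE, so the CRF-only route is empty.
- Only the fourth column leaves it any content. That reading takes protocol-defined to mean the 3.7.2 list alone and paracentesis to be not surgical. The exposure is then treated rises below 10 mmHg with no other listed event.
- The 1-hour outcome covers part of that band. It misses smaller rises and later ones, and it counts a rise without saying whether it was treated.

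Rises in this band can still be high in absolute terms. Assume that baseline IOP lies in the 21 to 35 mmHg entry range (1.7.1 item 5). A rise just under 10 mmHg then takes the eye to just under 21 + 10 = 31 mmHg at the low end and just under 35 + 10 = 45 mmHg at the high end.

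**2. Effect on the any-AE percentage.** Section 1.4 allows up to 20 consented subjects, so at most 20 are treated. Let n be the number treated and x the number of subjects whose treated rise is filed on the CRF only and who have no other AE. The shift is 100 × x/n.

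- Per subject: 1/20 = 5.0 points; 1/15 = 6.7 points; 1/10 = 10.0 points. The sizes 15 and 10 are assumptions.
- At n = 20, with x assumed to run from 0 to 4, the shift is 0, 5, 10, 15 or 20 points. The documents do not give x, and it may be zero.
- Example, assuming that 5 of the other 19 subjects have an AE: 5/20 = 25.0% with the CRF-only route and 6/20 = 30.0% with the AE route. If the subject already has another AE, the shift is 0.
- For scale, the exact (Clopper-Pearson) 95% interval for 1/20 runs from the 0.025 quantile of Beta(1, 20) to the 0.975 quantile of Beta(2, 19), that is 0.1% to 24.9%. One subject's shift is small against the imprecision of the study.

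**The case against.** The strongest case on the other side is that item 3 defers to the AE rules and does not override them. It allows CRF-only recording solely when no protocol-defined AE exists. If 3.7.1 or 3.7.2 makes the rise an AE, the AE route applies, and a fallback that is never used does no harm. This stands as far as it goes. A site that reads 3.7.1 as written records every treated rise. But a route that can never apply invites a site to find a case for it.

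A second argument is that the need-for-treatment limb of 3.7.1 cannot be read alone, because every subject enters on glaucoma medication and would have an AE at entry. So some qualifier, such as new or clinically significant, must be read in, and an insignificant rise would fall outside. The first half is fair. The second is strained: a postoperative rise is new, and one judged to need an anterior-chamber tap is hard to call insignificant. Where the protocol exempts early findings, it says so: cells and flare below 3+ within 30 days (3.7.1 item 2) and mild to moderate corneal edema through Week 1 (3.7.2). No such exemption for a treated pressure rise appears in 3.7.

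Third, the information is collected. Both routes put the paracentesis on a CRF, 3.9 summarizes IOP change at each evaluation, and 1.5.2 lists procedure-related complications. This stands: no data are lost. What is missing is a commitment to count the paracenteses, and the AE-specific information and follow-up.

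A reader might infer that the plan under-reports pressure-related AEs, or that large rises can escape. The documents support neither. Rises of 10 mmHg or more are listed AEs whether treated or not, and nothing shows that any site used the CRF-only route.

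**Conclusion.** On the visible text, item 3 of 3.3 Postoperative Instructions is inconsistent with 3.7.1 or has no content. Read with 3.7.1, the CRF-only route should never apply. If it is used, treated rises below 10 mmHg go unrecorded as AEs and miss the grading, relatedness and follow-up that AEs receive.

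Under-counting is therefore possible but not demonstrated. It depends on a site taking only the 3.7.2 list as protocol-defined and paracentesis as not surgical. The number of subjects is unknown. At the maximum of 20 treated, each one is 5.0 points of the any-AE rate, and only if that subject has no other AE. No hypothesis test or decision threshold in the visible text turns on that rate.

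Some sections are redacted, including text just before these instructions, and the CRFs are not in the documents, so a clarification may exist elsewhere. Severity is minor. The point is worth making because safety is the objective and the remedy is cheap.

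**What to change.** Delete the CRF-only route from item 3 of 3.3 Postoperative Instructions. In substance: if a pressure rise is judged to need paracentesis, record the rise as an AE with the IOP that prompted the procedure, and record the paracentesis as its treatment under 3.7.1 item 4. State in the same place that item 4 covers paracentesis. Because item 4 already bars the treatment from being a separate AE, nothing is counted twice.

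Add to the 3.9 safety summaries the number and percentage of subjects who had a paracentesis.

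The cost is a short rewording and one table row, from data already due on a CRF. Clinical management does not change. The downside is a possibly slightly higher AE percentage.

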3.4.1 Preoperative

- Screening Visit 1 (range 1 30 days prior to Baseline)
- Baseline Visit 2 (range 3 to 60 days prior to Operative)

3.4.2 Operative

• Surgery – Visit 3 (Day 0 occurring ≥ 3 days and ≤ 60 days after Baseline)

3.4.3 Postoperative

- Day 1 Visit 4 (1-day post-op)
- Week 1 Visit 5 (range 5 9 days post-op)
- Month 1 Visit 6 (range 21 35 days post-op)

- Month 3 Visit 7 (range 70 105 days post-op)
- Month 6 Visit 8 (range 168 196 days post-op)
- Month 12 Visit 9 (range 330 420 days post-op)

3.5 Schedule of Visits and Clinical Assessments

All required clinical assessments should be performed at each scheduled visit as specified in Appendix A. Methods for performing assessments are described in Appendix B.

For interim visits, clinical assessments that are required by the protocol or as deemed necessary by the Investigator will be conducted. Assessments will be performed according to methods described in Appendix B and recorded on an interim visit CRF. Unscheduled visit clinical assessments will be conducted according to standard of care and documented on an unscheduled visit CRF.

3.6 Subject Accounting Procedure

All consented subjects will be accounted for as follows:

- 1. Subject completion Subjects are considered to have completed the study if they have completed follow-up examinations through and including 6months.
- 2. Screen Failure Subjects are not considered enrolled in the study until they undergo surgery. Subjects are considered screen failures if they fail to meet screening criteria or baseline criteria as outlined in Section 1.7, or if they withdraw consent.
- 3. Early exit of enrolled subjects Subjects may be exited from the investigation in the event of a condition that may cause them harm if participation were to be continued. Subjects may also withdraw voluntarily.
- 4. Subject lost to follow up Subjects who do not return for their postoperative study visits and cannot be contacted within a reasonable timeframe via letter or telephone, will be considered lost to follow-up. The site will make at least three (3) telephone calls to the subject. If the three telephone contacts are unsuccessful, the site will send a registered letter with return receipt to the subject. The letter will request the subject to contact and return to the study site. If the subject is unresponsive to the first letter, the site will send a second registered letter with return receipt to the subject notifying them that they have been exited from the study due to lack of response on the part of the subject to the telephone calls and first registered letter. The site will then exit the subject from the study and the subject considered lost to follow- up. All attempts at contacting the subject (including telephone call logs, copies of registered letters and registered letter receipts) must be documented and maintained with the subject's study source documentation.

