1.1.2 Study Architecture

Study Architecture	
Study Design	This is a prospective, single-center, and single arm clinical trial of ViaLase Laser for the treatment of primary open angle glaucoma. Subjects will be screened for qualification as per the inclusion/exclusion criteria and must meet the inclusion/exclusion criteria in at least one eye to be enrolled. Up to 20 subjects will be consented as per the informed consent process. Subjects will be treated with the ViaLase Laser in one eye and followed for up to 12 months.
	Subjects will be screened for eligibility and informed consent will be obtained from consecutive subjects who meet screening criteria and are willing to participate in the study. Eligible subjects will be examined preoperatively to obtain a medical history and to establish a baseline ocular condition. Baseline and postoperative measurements will include distance visual acuity, manifest refraction, diurnal intraocular pressure, slit-lamp examination, gonioscopy, visual field, dilated fundus examination, specular microscopy, and pachymetry.
	Patient will continue use of IOP-lowering medications prior to surgery and up to 1 month post-operatively. The investigator has discretion to add, continue or remove medication thereafter.
	This study is being conducted in accordance with good clinical practice (GCP). Protocols have been submitted to and approved by an Ethics Committee for a study in patients freely providing informed consent. Data reporting, adverse event reporting and data collection is described in this protocol.
Study Location	Semmelweis University, Budapest, Hungary

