1.3 Study Objective

To obtain initial evidence of safety of image guided, femtosecond laser glaucoma surgery using the ViaLase Laser for the treatment of primary open angle glaucoma. The ViaLase Laser is intended to create apertures through the trabecular meshwork for drainage of aqueous humor in the treatment of open angle glaucoma.

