1.4 Study Design

This is a prospective, single-center, and single arm clinical trial of ViaLase Laser for the treatment of open angle glaucoma. Subjects will be screened for qualification as per the inclusion/exclusion criteria and must meet the inclusion/exclusion criteria in at least one eye to be enrolled. Up to 20 subjects will be consented as per the informed consent process. Subjects will be treated with the ViaLase Laser in one eye and followed for 12 months.

Eligible subjects will be examined preoperatively to obtain ocular and medical history and to establish a baseline ocular condition. Baseline and postoperative measurements will include distance visual acuity (best corrected), manifest refraction, intraocular pressure (IOP at baseline, 6 months and 12 months required), slit-lamp examination, gonioscopy, visual field, dilated fundus examination, specular microscopy (at baseline, 6 months and 12 months), and pachymetry.

Subjects who are on IOP lowering medications will be allowed to continue prior to laser treatment and up to one-month post-treatment. It is the investigator's discretion whether to add, continue or stop the medications after one month.

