1.5 Safety Outcomes

Safety outcomes are assessed immediately after laser surgery and over 12 months after surgery.

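### Safety follow-up is stated as 12 months, but Appendix A schedules no adverse-event enquiry at Month 12 and Section 3.6 sets completion at Month 6

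*Combined protocol and SAP*

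**What the plan says.** **Objective.** Section 1.3 gives one aim: "To obtain initial evidence of safety of image guided, femtosecond laser glaucoma surgery using the ViaLase Laser".

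**Twelve months.** Section 1.5: "Safety outcomes are assessed immediately after laser surgery and over 12 months after surgery". Section 1.4: "Subjects will be treated with the ViaLase Laser in one eye and followed for 12 months". Section 3.4.3 lists a Month 12 visit at days 330 to 420, Appendix B.9 asks for specular microscopy at 12 months, and Appendix A places the exit at Month 12. The synopsis (Section 1.1.2) is softer: "Subjects will be treated with the ViaLase Laser in one eye and followed for up to 12 months".

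**Six months.** Section 3.4, Examination Schedule: "Follow-up visits (as shown in Appendix A) will be scheduled over the course of 6 months". Section 3.6 item 1 counts as completers those who have "completed follow-up examinations through and including 6months".

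**Loss to follow-up.** Section 3.6 item 4 covers "Subjects who do not return for their postoperative study visits and cannot be contacted within a reasonable timeframe via letter or telephone". It has no Month 6 limit.

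**Adverse-event assessment.** Section 1.5.2 names adverse events among the long-term safety outcomes. In Appendix A the assessment is marked at Screening, Baseline, Day 0, Day 1, Week 1, Month 1, Month 3 and Month 6. Month 12 is blank.

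**Visual acuity.** Best spectacle corrected visual acuity (BSCVA) is marked in Appendix A at Baseline and Month 12. Footnote 2 adds it at Months 1, 3 and 6 only after a loss of at least 10 letters of corrected acuity. Appendix B.2 places it at Baseline and Month 6.

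**The concern.** In a study whose only stated purpose is safety, the final visit is where events since Month 6 should be asked about. A site that follows Appendix A to the letter has no adverse-event enquiry to make there. Section 3.9 plans to report how many patients had any adverse event, and what percentage they are. An event that is never asked about, and is the patient's only one, lowers that percentage.

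The completion rule raises a separate question, about reported retention. If completion means Month 6, the completion count does not say how many subjects reached the 12-month safety visit. A subject who disappears in between fits two categories of Section 3.6, and no rule says which applies.

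**Working it through.** The plan states no figure on this point to reproduce. The check compares the sections and applies simple arithmetic to the visit windows.

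**1. Is the blank cell real?** The adverse-event row of Appendix A has nine cells, one per visit column: eight are marked and the ninth, Month 12, is empty. The exit row in the same table has its single mark in the ninth column. The columns therefore line up, and the blank does not look like a fault in reading the table.

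**2. Time covered by no scheduled enquiry.** Inputs from Section 3.4.3 and Appendix A: Month 6 window, days 168 to 196; Month 12 window, days 330 to 420.
- Shortest gap: 330 − 196 = 134 days, which is 134/330 = 40.6% of follow-up.
- Longest gap: 420 − 168 = 252 days, which is 252/420 = 60.0%.
- Nominal gap: 365 − 182 = 183 days, which is 183/365 = 50.1% (182 is the middle of the Month 6 window).

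A mark at Month 12 reduces each of these to zero, because the enquiry would look back over the interval.

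**3. What would still be captured in that interval.**
- Section 3.7.1 requires events during the trial to be documented and asks staff to stay alert throughout.
- Section 3.7.3 requires serious events to be reported within 24 hours of the investigator learning of them. Section 3.7.4 allows at most 10 working days for unanticipated device effects. Neither depends on a visit mark.
- Section 3.7.5 keeps related systemic events and all eye events under follow-up, for up to one month after exit.
- Sections 3.4 and 3.5 require a report form for every interim and unscheduled visit.
- Appendix A marks nine examinations at Month 12 (corrected acuity, refraction, BSCVA, endothelial density, slit lamp, diurnal pressure, gonioscopy, fundus, pachymetry) and two medication reviews.

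These cover events that are serious, persistent, treated or visible on examination. What remains is mainly events that resolved without treatment and showed only as symptoms. An example is eye pain that settled before Month 12: Section 3.7.2 lists lasting pain as a possible event, and no examination in Appendix A measures pain.

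**4. Effect on the planned summary.** If a missed event was the subject's only one, the percentage with any adverse event falls by 1/N. The ceiling on N is the number consented (Section 1.4): "Up to 20 subjects will be consented as per the informed consent process". So the fall is at least 1/20 = 5.0 points per subject.

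**5. Effect on the completion figure.** Take a subject last seen at Month 6 and then lost. Item 1 of Section 3.6 is met, and so is item 4. Counting the subject as a completer overstates 12-month completion by 1/N:
- N = 20 (the most possible): 5.0 points.
- N = 15 (assumed): 6.7 points.
- N = 10 (assumed): 10.0 points.

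The documents give no expected loss rate, so the total overstatement cannot be computed. It is zero if nobody is lost after Month 6.

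**6. BSCVA.** Of the five postoperative visits through Month 6 (Day 1, Week 1, Months 1, 3 and 6), Appendix A gives none an unconditional BSCVA. On that table, a Month 6 completer can have no postoperative BSCVA. On Appendix B.2 the same subject would have one. The two cannot both stand.

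**The case against.** The other side has a good deal to say.

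- **The blank cell overrides nothing.** Section 3.5 tells sites to perform the assessments in Appendix A, but no clause lets an empty cell displace Section 3.7.1. A reader might infer that adverse events are not collected after Month 6, or that the interval is unobserved. The documents do not support that. Recording stays in force and the Month 12 visit is a full examination. This stands, and it limits the gap to a missing scheduled enquiry.
- **The class of events at risk is small.** Section 3.7.1 counts only conditions that are clinically significant or need treatment. After day 30, eye findings with a standard grading scale need a two-grade worsening, and the slit-lamp examination is marked at Month 12. This also stands. It does not remove significant symptoms that have resolved, and the rules for serious and unanticipated events start only once the investigator knows of them.
- **Later losses are not hidden.** Item 4 requires documented calls and letters and then records the subject as lost. A reader might infer that the completion rule conceals dropout or biases a result. It does neither: the loss appears under item 4, and Section 3.9 is descriptive, uses available results and defines no completer analysis set. What is missing is a rule of precedence between items 1 and 4.
- **Six months may be the intended core.** The softer synopsis wording, the 6-month effectiveness endpoint in Section 1.6 and Appendix B.2 point that way. But Sections 1.4 and 1.5 and the Month 12 exit visit are explicit, so the text contradicts itself on either reading.

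**Conclusion.** The contradiction is real and should be fixed, but it is of moderate weight. As written, no adverse-event enquiry is scheduled for the last 134 to 252 days of a 12-month safety study. The likely loss is confined mainly to resolved, untreated, symptom-only events. Its direction is known, since missed events can only lower the percentage of patients with any adverse event. Its size is not, because the documents give no rate for such events.

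The completion rule affects one reported number. It overstates 12-month completion by at least 5 points for each subject lost after Month 6, and changes no estimate. This rests on at most 20 treated subjects and on item 1 being applied as worded. The BSCVA conflict is a secondary inconsistency and does not carry the point.

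**What to change.** 1. In Appendix A, mark the adverse-event assessment at Month 12.
2. In Section 3.6 item 1, define completion as the Month 12 visit. State that a subject who leaves after Month 6 counts as early exit or lost to follow-up and not as a completer, and report retention at Month 6 and Month 12 separately. Bring the follow-up length in Section 3.4 into line with 12 months.
3. Reconcile Appendix B.2 with Appendix A on when BSCVA is measured.

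Items 1 and 2 are one table mark, one definition and one corrected duration, with no new visit or examination. Item 3 is a reconciliation of wording. The cost is a protocol amendment needing ethics committee approval, and possibly a less favourable completion figure.
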